### 1.3. CCR2 Inhibitor CCX140-B: Non-Clinical Safety

The nonclinical safety of CCX140-B was studied in vitro and in vivo in mice, rats, dogs and Cynomolgus monkeys.

In repeat dose toxicity studies (up to 26 weeks in rats and 39 weeks in dogs) two adverse nonclinical findings of concern were revealed:

- Anemia (red blood cell [RBC] parameter findings, with reticulocytosis) was observed across all species studied; rapid recovery of the RBC findings and reticulocytosis was observed following discontinuation of treatment.
- Peripheral axonopathy was observed at high exposures only in dogs; histological findings showed a likely cessation of active damage with decreased immune cell infiltrates following discontinuation of treatment; however, recovery was incomplete during the observation period.

The NOAEL in the 26-week rat studies of 15 mg/kg/day (based on reversible anemia) was associated with systemic AUC0-24 total plasma exposures to CCX140 of 464.6 and 493.7 µg•hr/mL, for males and females, respectively, and the Cmax concentrations was 32 µg/mL. The NOAEL in the dog studies (based on neuropathy) is higher than the NOAEL established in rat. Thus, for dose escalation in human subjects, the more sensitive rat-based NOAEL will be used: total plasma AUC0-24 exposures of 465 µg•hr/mL, with total Cmax exposures of 32 µg/mL. These exposures are approximately 3- to 4-fold higher than the predicted human exposures with a 15 mg twice daily (b.i.d.), the highest dose of CCX140-B to be tested in the current study.

Anemia findings are likely translatable to humans, but are verifiable, reversible, and there was an acceptable safety margin across all species (see below). To ensure early detection of anemia in the Phase 2 clinical trial, blood samples will be drawn at baseline, at 6 hours following administration of the first dose, at Study Days 8, 15 and 29, then at every 4 week intervals throughout the treatment and follow up period for assessment of complete blood count, reticulocyte count and bilirubin.

Neuronal findings were observed only in dogs, and may not be translatable to humans. Specifically, in the 39-week dog study, the highest tested dose of CCX140-B was associated with slight to mild neuronal cell changes on histology, with no clinically-observable changes. Off-target binding assays, in vivo immune mechanism assessments, and immunohistochemistry evaluations did not reveal a mechanism, but may rule out direct CCR2 receptor inhibition. In in vitro assessments, there were no metabolites that were unique to dogs, but there was a higher percentage of free CCX140 in plasma in dogs which was unique among studied species, including humans. Thus a threshold effect of free drug concentration cannot be ruled out. Subjects in the Phase 2 study will be monitored for adverse events related to the nervous system, and will be evaluated for early symptoms using a questionnaire validated for early detection of peripheral neuropathy in studies of patients with HIV infection.

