## Dose and Dose Adjustments

Eligible subjects will start treatment with CCX140-B at 5 mg twice daily. CCX140-B will be taken orally without food, at least one hour before a meal. The dose may be increased in a stepwise manner to 10 mg twice daily on day 15, then to 15 mg twice daily on day 43 while monitoring efficacy, PK and safety. Dose escalations will occur in accordance with the rules and schedule detailed in [Table 1](#), [Figure 1](#) and [Section 7.5.1](#). Dose may be adjusted downward in the event of intolerance, laboratory evidence of toxicity, or a measured or projected steady state exposure that exceeds the pre-specified maximum safe exposure based on the No Observed Adverse Event Level (NOAEL) established in the non-clinical toxicology program.

In all subjects, treatment at the selected dose will be continued through 12 weeks or until declaration of Treatment Failure, where Treatment Failure is defined as any of the following:

- 1) Progression of renal disease, defined as eGFR that is both below 60 ml/min/1.73 m^2 and is confirmed to represent at least a 30% decline in eGFR from baseline;
- 2) Requirement for rescue with glucocorticoids, other new immunomodulatory or immunosuppressive therapy, plasmapheresis, or dialysis, per the judgment of the Investigator;
- 3) Pre-specified adverse event or laboratory abnormality that, per Protocol, requires permanent discontinuation of study CCX140-B
- 4) Any other treatment-related adverse event, laboratory evidence of toxicity, or intolerance that, in the judgment of the Investigator, warrants permanent discontinuation of CCX140-B.

If planned dose escalation to 10 mg (on day 15) or 15 mg twice daily (on day 43) was previously halted the dose may be escalated further if subjects are not considered treatment failures and who otherwise meet criteria for continuation. In such case the subject will return approximately 2 weeks later for blood draws to assess PK (AUC0-6). Subjects will return 2 weeks after the PK assessment to evaluate the safety and need for further dose adjustment.

Subjects who completed 12 weeks of treatment are not considered treatment failures and who otherwise meet criteria for continuation may be extended for up to an additional 40 weeks to assess degree and duration of response. During the extension period the dose may be adjusted if indicated based on assessment of safety, PK and efficacy. (see [Table 1](#) and [Figure 1](#) for

guidelines).

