**Table 1: Dose Modification Schedule and Rules Through Study Day 85**

Study Day	Dose and Requirements for Dose Modification
1	Initiate dosing at 5 mg twice daily
15	At Day 15, dose will be increased to 10 mg twice daily if all of the following are true: 
 
• Subject has not achieved and maintained at least Partial Remission and
 
• Subject is not a Treatment Failure
 

29	At Day 29, PK samples will be collected to measure AUC 0-6 and enable projection of AUC 0-12 at both the current dose level and the next higher planned dose level AUC 0-12
43	At Day 43 based on results of the Day 29 PK, the dose may be adjusted to the next higher planned dose level (15 mg twice daily for subjects receiving 10 mg twice daily; 10 mg twice daily for subjects receiving 5 mg twice daily) if all of the following are true: 
 
• Subject is not a Treatment Failure, and
 
• Meets all criteria for continuation:               
 
○ Subject has not achieved and maintained at least a Partial Remission, and
 
○ Projected AUC0-12 on the next higher planned dose level does not exceed 240 <math>\mu\text{g}\cdot\text{h}/\text{mL}</math> and
 
○ The next higher dose does not exceed the Maximum Tolerated Dose (MTD)
 
 
 
 NOTE: If the projected AUC 0-12 on the current dose exceeds 240 $\mu\text{g}\cdot\text{h}/\text{mL}$ , dose will be de-escalated to the next lower dose level
57	At Day 57, PK samples will be collected to measure AUC 0-6 and enable projection of AUC 0-12
Day 71	Based on results of Day 57 PK, subjects can be considered for dose escalation if all of the following are true: 
 
• Subject is not already treated with 15 mg twice daily and
 
• Subject did not require previous downward dose adjustment and
 
• Subject is not a Treatment Failure, and
 
• Meets all criteria for continuation:               
 
○ Subject has not achieved and maintained at least a Partial
 
 
 

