### 6.2. Study Day 1 (After Confirmation of Eligibility)

**All evaluations on day 1 (unless otherwise specified in the Day 1 section) will occur PRIOR to dosing to serve as baseline evaluations.**

1. Enroll study subject and obtain enrollment ID code
2. Full Physical Examination and Vital Signs including height, weight, heart rate, respiratory rate and body temperature
3. 24 hour urine collection for UPCR, UACR and total protein. *Subject starts 24hr. collection after the first void in the morning of the day prior to the visit day and should bring the 24hr collection (including first morning void on the visit day) to the visit. Sites need to contact the subject prior to the visit day as a reminder to start the 24 hr. urine collection*
4. AIDS Clinical Trials Group Brief Peripheral Neuropathy Screening Tool (ACTG BPNST)

5. Leg circumference and bioimpedance to assess edema
6. Triplicate 12-Lead ECG
7. Pregnancy Test for women of childbearing potential
8. Hematology, Serum Chemistry, Urinalysis
9. 24 hour urine collection for UPCR, UACR and total protein. *Subject starts 24hr. collection after the first void in the morning of the day prior to the visit day and should bring the 24hr collection (including first morning void on the visit day) to the visit. Sites need to contact the subject prior to the visit day as a reminder to start the 24 hr. urine collection. Please be reminded that a 24 hr. urine collection at baseline (Study day 1) and at week 12 are mandatory.*
10. SF-36 v2 and EQ-5D-5L
11. Dispense diaries and *Directions for Use* along with a 30 day supply of CCX140-B bottles.
12. Pharmacokinetics (time 0, 0.5, 1, 2, 3, 4 & 6 hours post dose), the time 0 sample is to be collected just prior to administration of the first dose of CCX140-B. Subjects must fast prior to the time 0, 0.5 and 1 hour PK and can consume food immediately after the 1 hour PK blood draw.
13. PD (plasma, serum and urine and whole blood for the lymphocyte subset and DNA)
14. Concomitant medications- verify and document any new medications that subject has started since the previous visit.
15. Adverse Events- record all adverse events starting with first dose of study medication and serious adverse events starting after administration of Informed Consent.

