### **6.3. Study Day 15 (Safety, Efficacy and PK)**

1. Symptom directed abbreviated physical examination and vital signs including weight, heart rate, respiratory rate and body temperature.
2. AIDS Clinical Trials Group Brief Peripheral Neuropathy Screening Tool (ACTG BPNST).
3. Leg circumference and bioimpedance to assess edema
4. Hematology, Serum Chemistry, Urinalysis
5. 24 hour urine collection for UPCR, UACR and total protein. *Subject starts 24hr. collection after the first void in the morning of the day prior to the visit day and should bring the 24hr collection (including first morning void on the visit day) to the visit. Sites need to contact the subject prior to the visit day as a reminder to start the 24 hr. urine collection*
6. Review diary and used study medication with each subject. Confirm dosing compliance.
7. Pharmacokinetics ( $C_{min}$ ) – sample is to be collected at time 0 (just prior to taking the first dose of 10 mg CCX140-B)
8. PD (plasma, serum and urine and whole blood for the lymphocyte subset). Samples are to be collected at time 0.

9. Concomitant medications- verify and document any new medications that subject has started since the previous visit.
10. Adverse Events- record all adverse events starting with first dose of study medication.

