### 7.2. Clinical Safety Laboratory Assessments

The following tests will be performed at the visits identified in the [Time and Events Table](#).

**Hematology:** hemoglobin, hematocrit, RBC count, WBC count with differential, platelet count, mean cell hemoglobin, mean cell hemoglobin concentration, mean corpuscular volume, haptoglobin and schistocytes.

**Serum Chemistry:** liver panel (total and direct bilirubin, lactate dehydrogenase [LDH], AST, ALT), renal panel (BUN, creatinine), creatine phosphokinase (CPK), albumin, sodium, potassium, magnesium, bicarbonate, chloride, calcium, inorganic phosphorus, glucose, total protein, alkaline phosphatase, coagulation panel (PT, PTT, INR), lipid panel (HDL, non-HDL LDL, Triglycerides, Total Cholesterol), uric acid, serum amylase, serum lipase, LDH and cystatin C.

**Urinalysis:** At the central laboratory, nitrite, blood, and protein, will be tested. If positive, microscopy will be performed.

**Virology** (measured only at screening and may be measured at the local laboratory): hepatitis B surface antigen, hepatitis C antibodies, HIV 1 and 2 antibodies; virology tests done within 6 weeks prior to screening are acceptable for eligibility assessment.

**TB screen:** Only one of the following is needed: interferon  $\gamma$  release assay (IGRA), tuberculin purified protein derivative (PPD) skin test, or chest radiograms (X rays or CT scan); chest radiography done within 6 weeks prior to screening is allowed for eligibility assessment. Chest radiography at subsequent visits will only be performed if deemed clinically necessary by the Investigator to assess safety.

**Pharmacodynamics:** urinary MCP-1, and potentially other biomarkers of renal inflammation, fibrosis and injury. Assessment of blood and/or urinary biomarkers associated with CCR2 biology, which may include peripheral blood leukocyte subsets and selected cytokines and chemokines.

**Genetic Markers:** Assessment of biomarkers associated with risk of severity of disease, which may include allelic variations associated with the pathogenesis and/or prognosis of FSGS such as NPHS1, NPHS2, WT-1, LAMB2, CD2AP, TRPC6, ACTN4, INF2, APOL1.

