#### 7.5. Dose Modification Rules

**Table 2: Dose Modification Rules for Individual Subjects**

Assessment	Event	Timing	Response
Serum Creatinine	50% increase from baseline value	If confirmed by repeat measurement after 2 weeks	If confirmed by repeat measurement after 2 weeks
Urine Protein:Creatinine ratio (UPCR)	If baseline UPCR < 6.0 g/g an increase of > 3.0 g/g; if UPCR $\geq$ 6.0 g/g an increase of 50%	If confirmed by repeat measurement after 2 weeks	If confirmed by repeat measurement after 2 weeks
ALT, AST	ALT or AST $\geq$ 8x ULN	Confirmed within 72 hours (ALT, ASP, ALP and Total Bilirubin should all be re-tested)	Consider Discontinuation of Treatment
ALT, AST	ALT or AST $\geq$ 5x ULN	Confirmed within 2 weeks (ALT, ASP, ALP and Total Bilirubin should all be re-tested)	Consider Discontinuation of Treatment
ALT, AST, Total	ALT or AST $\geq$ 3x	Confirmed within 72	Consider Discontinuation of

Bilirubin and INR	ULN and Total Bilirubin > 2 ULN or INR > 1.5	hours (ALT, ASP, ALP, Total Bilirubin and INR should all be re-tested)	Treatment
ALT, AST	ALT or AST $\geq$ 3x ULN with the appearance of fatigue, nausea, vomiting, right upper quadrant pain or tenderness, fever, rash and /or eosinophilia (>5%)	Confirmed within 72 hours (ALT, ASP, ALP and Total Bilirubin should all be re-tested)	Consider Discontinuation of Treatment
Hemolysis	Clinical diagnosis of hemolysis in the judgment of the investigator, based on elevation of LDH, elevation of reticulocyte count, elevation of bilirubin and or other laboratory indications.	Halt treatment then reassess after 1 week	If normalized, continue to treat at reduced dose, defined as the next lower dose. Otherwise, contact Medical Monitor to discuss next steps
Anemia	Hemoglobin reduced from baseline by $\geq$ 2 g/L and deemed clinically significant by the PI	Halt treatment then reassess after 2 weeks	If normal, continue to treat at reduced dose, defined as next lower dose. Otherwise, contact Medical Monitor to discuss next steps
Reticulocyte Count	Increase in reticulocyte count by $\geq$ 2% (absolute) from baseline that is not otherwise explained	Halt treatment then reassess after 2 weeks	If within normal range for the hematocrit, continue to treat at reduced dose, defined as next lower dose. Otherwise, contact Medical Monitor to discuss next steps

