### Subject Instructions for Dosing of Study Medication on Visit Days

On the day of each study visit, the subject should not take their morning study medication until they get to the clinic. They will then take it in the presence of the study staff. On the days when they do not have a study visit, they will take their first dose of study medication in the morning at approximately the same time each day. Their second dose should be taken approximately 12 hours after the first dose.

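### Protocol Section 1.3 commits to anemia blood counts at 6 hours and on Day 8, but no schedule contains them: 2 post-dose counts promised before the day of the first dose increase, 0 scheduled

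*Protocol*

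**What the plan says.** - **The commitment.** Protocol Section 1.3 states that "blood samples will be drawn at baseline, at 6 hours following administration of the first dose, at Study Days 8, 15 and 29" and every 4 weeks after that. The tests are complete blood count, reticulocyte count and bilirubin, and the stated purpose is early detection of anemia.
- **Day 1.** Under Protocol Section 6.2, Day 1 evaluations, unless otherwise specified, "will occur PRIOR to dosing to serve as baseline evaluations". The hematology and chemistry item carries no post-dose time. The only timed post-dose blood samples, which run to 6 hours, are for pharmacokinetics (PK).
- **Day 8.** The Time and Events Table has no Day 8 column, Section 6 goes from Day 1 (6.2) to Day 15 (6.3), and SAP Section 3.6.2 lists Day 1 and then Day 15. Protocol Section 3.1 and SAP Section 2.2.1 do speak of weekly visits while the dose is being escalated.
- **Day 15.** Table 1 reads "At Day 15, dose will be increased to 10 mg twice daily if all of the following are true", and the two conditions are no maintained Partial Remission and no Treatment Failure. The trough PK sample is taken "just prior to taking the first dose of 10 mg CCX140-B" (Section 6.3). On visit days, according to Appendix A, "the subject should not take their morning study medication until they get to the clinic".
- **Halt rules.** For anemia and for a raised reticulocyte count, Table 2 says "Halt treatment then reassess after 2 weeks". The laboratory item in the Treatment Failure definition is narrower: "Pre-specified adverse event or laboratory abnormality that, per Protocol, requires permanent discontinuation of study CCX140-B".
- **Panel.** The hematology list in Section 7.2 ends with "mean cell hemoglobin concentration, mean corpuscular volume, haptoglobin and schistocytes" and does not name the reticulocyte count.

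**The concern.** Anemia is the toxicity that the sponsor itself singles out. Section 1.3 reports it in every species studied, bases the rat NOAEL on it, and regards it as likely to carry over to humans. Section 5.2.1 relies on the Time and Events Table for early detection of dose-related signals. A site that follows that table and Section 6 would take no count between the first dose and the visit at which the daily dose doubles to 20 mg. That is above the highest daily dose reported from completed studies (15 mg, Section 1.6). The Table 2 anemia and reticulocyte rules can act only once a count exists.

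At stake are an undelivered safety commitment and the risk that a study report repeats the Section 1.3 schedule as if it had been carried out. The Week 12 efficacy summary is not affected.

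**Working it through.** This is a count of scheduled draws; no power or error-rate formula applies.

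| Time | Protocol 1.3 | Time and Events Table | Protocol Section 6 | SAP 3.6.2 |
|---|---|---|---|---|
| Baseline | yes | Day 1 | 6.2, pre-dose | Day 1 |
| 6 hours | yes | PK sample only | 6.2, PK only | no |
| Day 8 | yes | no column | no visit | no |
| Day 15 | yes | yes | 6.3 | yes |
| Day 29 | yes | yes | 6.4 | yes |

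1. Post-dose counts before Day 15: promised 2 (6 hours, Day 8), scheduled 0.
2. Post-dose counts through Day 29: promised 4, scheduled 2.
3. Section 6 and SAP 3.6.2 are prose lists, so a table damaged in text extraction cannot explain the gap.

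**Drug taken before the first scheduled count** (5 mg twice daily, full compliance, sample before the morning dose, increase made at the visit):
- Day 15: 14 days × 2 = 28 doses; 28 × 5 mg = 140 mg.
- Visit window of 3 days either side: Day 12 gives 11 × 2 = 22 doses, 110 mg; Day 18 gives 17 × 2 = 34 doses, 170 mg.
- Under Section 1.3: after 1 dose (5 mg) at 6 hours, and after 7 × 2 = 14 doses (70 mg) on Day 8.

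**Size of the Day 15 step:** from 10 to 20 mg/day; 20 / 15 = 1.33 times the highest earlier daily dose. This is a ratio of doses, not of exposures. Section 5.2.1 reports exposure about 30% lower in subjects with heavy albuminuria. If that carried over in proportion, 20 × 0.7 = 14 mg/day equivalent, below 15. This is illustrative only.

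**Margins (Section 5.2.1):** rat NOAEL exposure is about 9-10 times human exposure at 10 mg once daily and 4-5 times that at 10 mg twice daily. The first of these is the relevant one while the missing draws would fall, because 5 mg twice daily is the same daily dose. The 5 mg paragraph of that section attaches 8-10 fold to 10 mg twice daily; the smaller figure is used here.

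**The case against.** **Section 1.3 is background and the operative schedule is consistent, so correcting one sentence would be enough.** That would remove the contradiction. It would also withdraw the plan's only stated early-detection measure for this toxicity, when restoring it needs one tube at an existing draw and one blood draw that the plan already promises.

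**The clinical risk is small.** This stands. The margins are those above, 10 mg once daily was tolerated for 52 weeks (Section 1.6), the red-cell findings recovered rapidly off treatment (Section 1.3), and the Day 15 and Day 29 counts both precede the Day 43 step.

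**Table 1 is not the only control.** This also stands. A reader might infer that the Day 15 increase has no safety check. The documents do not support that: the Synopsis ties increases to monitoring of efficacy, PK and safety, Section 3.1 names safety among four factors guiding dose changes, and Table 2 halts treatment for anemia, reticulocytosis or hemolysis. What remains is that no count is scheduled to feed those controls before the Day 15 visit.

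**The reticulocyte count was planned.** A reader might infer from Section 7.2 that it was not. The Synopsis safety endpoints, Protocol Section 2.3 and SAP Sections 2.1.2 and 2.3.5 all list it within hematology, so the Section 7.2 list is merely incomplete.

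**The weekly-visit wording covers Day 8.** It implies such a visit, but neither the table nor Section 6 contains one.

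**Conclusion.** The inconsistency holds: 0 of the 2 post-dose counts promised before Day 15 are scheduled, and the first scheduled one falls on the day of the first 10 mg twice-daily dose. It should be corrected before the protocol is used again, but the expected clinical impact is modest. The SAP (Sections 1 and 6) records that enrollment was not continued, so for subjects already treated only the reporting sentence is useful.

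Two stronger readings go beyond the documents:
- That the Day 15 result cannot be known before the 10 mg dose. This is plausible: SAP Section 3.6.2 sends hematology to a central laboratory, and the amendment rationale for the hepatic exclusion says that centrally tested Day 1 results come too late for Day 1 dosing. But no turnaround time is given, and the SAP also mentions local laboratory data.
- That the plan promised a blood-count condition for the Day 15 increase. Section 1.3 promises draws, not a condition.

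The conclusion assumes that sites follow Section 6 and the Time and Events Table. Unscheduled draws are possible, and the documents do not show what was actually drawn.

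**What to change.** 1. In the Time and Events Table and Section 6.2, add blood count, reticulocyte count and bilirubin to the existing 6-hour Day 1 draw, marked as post-dose.
2. In the Time and Events Table, Section 6 and SAP Section 3.6.2, add a Day 8 blood-draw-only entry for the same tests at the central laboratory, with results reviewed under the existing Table 2 rules before the Day 15 increase. A window of 1 day either side is advisable: the latest draw (Day 9) then precedes the earliest Day 15 visit (Day 12) by 12 − 9 = 3 days. The table's 3-day window would leave 12 − 11 = 1 day.
3. Add reticulocyte count to the Section 7.2 panel, in line with the Synopsis and Section 2.3.
4. In the abbreviated study report, state that the first scheduled post-dose count was on Day 15.

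Two changes should not be made. A new blood-count condition in Table 1 would rest on the Table 2 anemia threshold of 2 g/L, which is 0.2 g/dL and a tenth of the 2 g/dL in Section 7.5.1. Replacing the weekly-visit wording with two-weekly visits would drop the implied Day 22 and Day 36 visits, and Day 22 closes the first week at 20 mg/day.

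**Cost:** one extra tube and one short attendance per subject, at most 13 of each (26 samples), and none for subjects already treated. If a late review held back the increase, the PK sampling planned for Day 29, which feeds the Day 43 decision, would move with it. SAP Section 3.5 already allows that sampling at 14 days after 10 mg twice daily starts. No efficacy analysis changes, and the report sentence costs nothing.
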